Patients randomized to undergo TFESI will be placed supine on the CT gantry table. A planning CT scan (120 kVp, automatic tube current modulation: 100 – 400 mA, 2.5 mm section thickness, rotation time 0.5 seconds) will be obtained with z-axis limited to the area of interest. Acquired images will be used to plan a lateral approach needle trajectory, as previously described (9). The skin surface will then be marked, sterilized, draped, and anesthetized. A 22-gauge 1.5 or 3.5 inch Quincke tip spinal needle will be advanced under intermittent CT fluoroscopic guidance into the posterolateral aspect of the neuroforamen (Figure 1A). On reaching the target, gentle aspiration will confirm absence of blood return. Approximately 0.2 mL of contrast material (iopamidol; Isovue-M 200, Bracco Diagnostics, Princeton, NJ) diluted 1:3 with preservative free normal saline will then be injected to assess needle tip position and potential future medication spread. Intravascular injection is excluded using a “double-tap” technique (i.e., 2 sets of CT fluoroscopic images: an initial image immediately after injection and a second image acquired 2-3 seconds later to assess for contrast material washout), as previously described (10). After visual confirmation of safe needle tip positioning, a test injection of approximately 0.5 mL of 1% lidocaine will exclude symptoms suggestive of intra-arterial injection (alteration in sensation, motor weakness, metallic taste, seizure). Finally, 0.8 mL of dexamethasone (10 mg/mL) will slowly be injected over a period of approximately 30 seconds. On completion of the procedure, the patient will be observed for 30 minutes in the Radiology Observation unit.

Lateralized Interlaminar Epidural Corticosteroid Injections (LILESI)

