Patients randomized to undergo LILESI will be placed prone on the CT gantry table. A planning CT will be obtained through the area of interest. Acquired images will allow for planning a posterior approach lateralized interlaminar needle trajectory to the dorsal epidural space. The skin surface will then be marked, sterilized, draped, and anesthetized. A 22-gauge 3.5 inch Quincke tip spinal needle will be advanced under intermittent CT fluoroscopic guidance into the lateral dorsal epidural space (Figure 2). On reaching the target, heme-negative aspiration will be confirmed. Next, approximately 0.2 mL of contrast material (iopamidol; Isovue-M 200, Bracco Diagnostics, Princeton, NJ) diluted 1:3 with preservative free normal saline will be injected to assess needle tip position and potential future medication spread. Intravascular injection will be excluded using a “double-tap” technique. After visual confirmation of correct needle tip position, 0.8 mL of dexamethasone (10 mg/mL) will slowly be injected over a period of approximately 30 seconds. On completion of the procedure, the patient will be observed for 30 minutes in the Radiology Observation unit.

Patient Outcome Measures

Prior to the procedure, baseline outcome measures of NRS, NDI, EQ-5D and WAI will be determined (see Outcome Measures below for description). Immediately post-procedure, NRS will be reacquired. NRS, NDI, EQ-5D and WAI will then also be acquired via mail, electronic communication, or telephone call at 2 weeks, 2 months, and 4 months post-procedure. The primary endpoint will be NRS (averaged over the past 24 hours) obtained at 2 months after the procedure. Secondary endpoints will include NRS at 2 weeks and 4 months after the procedure as well as NDI, EQ-5D and WAI at 2 weeks, 2 months, and 4 months after the procedure.

Adverse Events

Patients will be screened for adverse events immediately after the procedure as well as via phone call at 2 days post-procedure. While all adverse events will be recorded, the following will be considered major adverse events: stroke, paralysis, or other permanent neurologic deficit; allergic reaction; hospitalization or ER visit. Minor adverse events will include, but not be limited to: nausea / vomiting, dizziness, headache, symptomatic hypertension, vasovagal reaction, fever / chills, facial flushing, insomnia, and pain exacerbation.

Epidurogram

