The pain numerical rating scale (NRS) is a well-validated tool for quantitatively assessing patients' pain (12). The NRS asks patients to rate their current pain intensity on an 11-point scale ranging from 0 ("no pain") to 10 ("worst possible pain"). It has been found to be a valid measure of pain intensity with minimum clinically important difference noted to be a change of 2 points (13, 14). We will use NRS averaged over the past 24 hours for all time points in this trial. The Initiative on Methods, Measurement, and Pain Assessment in Clinical Trials (IMMPACT) consensus statement indicates that an NRS reduction of 30% (or 2 points) is associated with a meaningful or moderately important improvement in pain. Further, IMMPACT also indicates that an NRS reduction of 50% (or 4 points) is associated with a substantial improvement in pain. We will follow their consensus recommendations and explicitly report these two categories of pain relief (15).

Neck Disability Index (NDI)

The NDI a well-validated measurement tool that contains 10 items: seven related to activities of daily living, two related to pain, and one related to concentration (16). Each item is scored from 0 to 5 and the total score is expressed as a percentage, with higher scores corresponding to greater disability. The NDI has documented acceptable levels of responsiveness and construct validity when used in patients with cervical radiculopathy (17).

EQ-5D

EQ-5D is a standardized measure of health status developed by the EuroQol Group in order to provide a simple, generic measure of health for clinical and economic appraisal (18). It is a well-validated tool for health status measurement (19), and for health quality-of-life in cervicogenic radicular pain (20).

Work Ability Index

The Work Ability Index (WAI) is a validated, reliable measure of a worker's ability to do his or her job that has been shown to predict work disability, retirement and mortality (21). The questionnaire demonstrates excellent test - retest reliability (22).

All data will be collected in a password-protected file and will be stored in an electronically secure environment, as specified in the research data security plan (RDSP).

Selection of Subjects

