Adult patients with unilateral cervicogenic upper extremity radiculopathy (with or without accompanying neck pain) and a baseline numerical pain scale (NRS) score > 4 will be recruited from the Duke Radiology and Orthopaedic spine intervention clinics. Exclusion criteria include: (a) recent (i.e., < 2 months) cervical spine surgery, (b) recent (i.e., < 1 month) cervical epidural or upper extremity corticosteroid injection, (c) contraindication or inability to undergo procedure, (d) inability to provide informed consent, (e) expected inability to complete follow-up assessment, or (f) a contraindication to receiving contrast material (precluding an epidurogram). We aim to recruit 116 patients over 1 year. This number is based on the historical number of patients treated with unilateral

cervical radiculopathy, our sample size determination (see Statistics), and previously published studies in the lumbar spine (7).

We estimate that approximately 1000 patients will be screened over one year in order to reach our target recruitment of 116 patients.

Subject Recruitment and Compensation

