Based on a power of 0.8 (alpha 0.05) to detect superiority of the LILESI group, assuming positive response rates of 45% for the TFESI group and 70% for the LILESI group, we would need a total of 116 patients (57.5 patients in each arm). This sample size would also give us a power of 0.99 to detect non-inferiority (i.e. equivalence between TFESI and LILESI) (non-inferiority margin 0.1).

Patient Outcome Analysis

A reduction of 2 points from baseline on the NRS will be considered a positive response (clinically meaningful or moderate improvement per IMMPACT consensus statement) (15). Primary Endpoint (average NRS over the past 24 hours at 2 months time point): We will apply a difference test and a non-superiority test for binomial proportion to test the primary endpoint. Secondary Endpoints: The secondary endpoints will be analyzed using a test for difference in binomial proportions or a t-test for binomial or semi-continuous variables, respectively.

Interim Data Analysis

An interim analysis will be performed of the first 58 patients by the biostatistician (co-investigator). All study participants, assessors, and other personnel (including other co-investigators) will remain blinded. Safety and efficacy will be evaluated using an O'Brien–Fleming stopping rule of $p < 0.001$ for the interim analysis in order to evaluate for early evidence of treatment efficacy (26).

Crossover, Withdrawal, or Missing Data

We will employ an intention-to-treat (ITT) analysis for this trial (27). Patients that crossover between study arms, withdraw from the study, or for whom there is missing data will all be handled in the same manner. A conservative approach will be taken and we will assume that the patient will receive no further benefit from the study injection. As such, the most recent available outcomes data will be extrapolated to all later time points for which no data are available.

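### The 24-hour recall period, as worded, also covers the NRS taken straight after the procedure, so that reading nearly repeats baseline; its recall period and its place in carry-forward need stating

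*Combined protocol and SAP*

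**What the plan says.** All references are to the combined protocol and SAP.

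- **Patient Outcome Measures** (Design & Procedures) has the NRS taken before the procedure and at 2 weeks, 2 months and 4 months. It adds one further reading: "Immediately post-procedure, NRS will be reacquired". That sentence gives no recall period and no clock time.
- **Outcome Measures, Numerical Rating Scale (NRS)** sets the recall period: "We will use NRS averaged over the past 24 hours for all time points in this trial". Earlier in the same paragraph the instrument is described differently: "The NRS asks patients to rate their current pain intensity on an 11-point scale". Nothing reconciles the two.
- **The two procedure descriptions** (TFESI, and lateralized interlaminar injection, LILESI) both end with the same stay: "the patient will be observed for 30 minutes in the Radiology Observation unit". Both include anesthesia of the skin. Only the TFESI description adds, once the needle is at the target, "a test injection of approximately 0.5 mL of 1% lidocaine".
- **Patient Outcome Analysis** defines response: "A reduction of 2 points from baseline on the NRS will be considered a positive response". **Selection of Subjects** requires "a baseline numerical pain scale (NRS) score > 4".
- **Crossover, Withdrawal, or Missing Data** (in the design part and again in the statistical part) fills missing time points with the latest outcome value on hand. It presents this as a conservative assumption of no added benefit. It does not exclude the immediate reading as a source.

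The immediate NRS appears in none of the aims, in neither endpoint list and in no planned analysis.

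**The concern.** A pain average over the last 24 hours, asked shortly after an injection, is almost wholly an average of pain before it. A patient who follows the wording gives nearly the baseline answer again, whatever the injection did. A patient who answers with present pain gives a different quantity, and one that could be affected by a local anesthetic described for one arm only. With both definitions in one paragraph, different patients may answer differently, and the column of data could not be interpreted afterwards.

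Most of this touches a reading that no analysis uses. The exception is carry-forward. For a patient with no NRS at 2 weeks or 2 months, the immediate reading is the most recent one, so it becomes the 2-month primary value. Whether that patient counts as a responder could then depend on which recall period was used.

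**Working it through.** The plan gives no figure for this reading, so there is none to reproduce. The check is what a time-weighted 24-hour average can show.

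**Inputs**
- Recall window: 24 h = 1,440 min (NRS section).
- Time from injection to reading: not stated. Assumed range 30 to 120 min; the 30-minute observation stay is a guide, not a documented limit.
- Baseline NRS: above 4 (Selection of Subjects), so whole-number scores 5 to 10.
- Response: a fall of 2 points from baseline (Patient Outcome Analysis).
- Pain before the injection: assumed steady at the baseline score.

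**Step 1: share of the window after the injection,** w = minutes / 1,440
- 30 min: 30/1,440 = 2.1%, so 97.9% is before the injection
- 60 min: 60/1,440 = 4.2%, so 95.8% is before
- 120 min: 120/1,440 = 8.3%, so 91.7% is before

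**Step 2: a worked case.** For a true fall from 7 to 2, recorded score = 7 − 5w.
- 30 min: 7 − 5 × 0.0208 = 6.90
- 120 min: 7 − 5 × 0.0833 = 6.58

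**Step 3: largest possible recorded fall,** with instant and complete relief = baseline × w

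| Baseline | 30 min | 60 min | 120 min |
|---|---|---|---|
| 5 | 0.10 | 0.21 | 0.42 |
| 7 | 0.15 | 0.29 | 0.58 |
| 10 | 0.21 | 0.42 | 0.83 |

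No cell reaches 2.

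**Step 4: hours of complete relief needed for a 2-point fall** = 24 × 2 / baseline
- Baseline 5: 48/5 = 9.6 h
- Baseline 7: 48/7 = 6.9 h
- Baseline 10: 48/10 = 4.8 h

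The conclusion therefore does not depend on the 30-minute figure.

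**Step 5: the carry-forward route.** With 116/2 = 58 patients per arm, one patient moves an arm's response rate by 1/58 = 1.7 percentage points. The non-inferiority margin is 0.1, or 10 points (Sample Size Determination). The plan gives no dropout rate. As an illustration only, three such patients in one arm would move its rate by 3/58 = 5.2 points. Under the literal 24-hour wording these patients are non-responders, by Step 3. Under a current-pain answer, any of them could be counted as a 2-month responder on the strength of a score taken on the day of injection.

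**The case against.** The best defense is that little depends on this reading. It belongs to no aim, endpoint, sample-size assumption or planned test, and the baseline, 2-week, 2-month and 4-month readings are properly defined. The instrument description supports a present-pain answer, the sentence that schedules the reading carries no recall period, and elsewhere the plan mostly uses the term time point for follow-up visits. On that view the recall period is unclear rather than wrong. This largely stands, and it sets the severity. It does not remove the problem, because the 24-hour sentence is universal and makes no exception.

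Two stronger readings are tempting, and the documents do not support them. One is that the reading defeats the purpose for which it is collected. No purpose is stated, and no immediate response rate is planned. The other is that a current-pain answer would show an anesthetic effect in the TFESI arm. The documents give neither size nor likelihood for such an effect. They support only that the arms could differ.

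A further objection also stands. Redefining the reading as current pain, with nothing more, could make matters worse. Under the 24-hour wording a carried-forward immediate score stays near baseline, which agrees with the plan's conservative intent. A current-pain score carried forward might not, and any resulting bias could depend on arm. The redefinition must therefore come with a bar on carry-forward.

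**Conclusion.** The point holds as a minor one. Followed literally, the plan collects an immediate NRS of which 92% to 98% describes pain before the injection, if the reading falls 30 to 120 minutes afterwards. It can fall by at most 0.83 points in that range, so it cannot register the plan's 2-point response. Answered as current pain, it could show a change but might not be comparable between arms. The figures rest on the assumed timing, steady pain beforehand and a true time-weighted average. Patients may not average so exactly, which is another reason to state the question plainly.

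A reader might infer that the primary endpoint is compromised. That does not follow. An observed 2-month NRS is unaffected, and so is a 2-month value carried forward from 2 weeks. The exposure is confined to patients with neither reading. Each is worth 1.7 percentage points in an arm of 58, and the documents do not say how many there will be.

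**What to change.** 1. Limit the 24-hour sentence in the NRS section to baseline, 2 weeks, 2 months and 4 months.
2. Define the immediate post-procedure reading as current pain. Ideally ask the same current-pain question just before the procedure, so that there is a like-for-like comparator.
3. Report the immediate reading descriptively by arm, with a note that only the TFESI description includes a lidocaine test injection.
4. State in both missing-data sections that this reading is never carried forward. Where no follow-up NRS exists, use the baseline 24-hour NRS, which counts as no response and keeps the plan's conservative intent.

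The cost is a few lines of wording and one or two form questions. The immediate reading will have a different recall period from the others and cannot be plotted on the same line as the 24-hour scores without a note. Item 4 should not be left out if item 2 is adopted.

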Comparison of cervical transforaminal epidural corticosteroid injections with lateralized interlaminar epidural corticosteroid injections for treatment of cervicogenic upper extremity radiculopathy

NCT03389620

Document Date: 11/15/2022

Purpose of the Study

Our central hypothesis is that the innovative CT fluoroscopy-guided lateralized interlaminar epidural corticosteroid injection technique will exhibit superior or equivalent efficacy to the traditional transforaminal method for treatment of cervicogenic upper extremity radiculopathy.

SPECIFIC AIM 1: Compare the efficacy of CT fluoroscopy-guided LILESI to that of CT fluoroscopy-guided TFESI in the treatment of patients with cervicogenic upper extremity radiculopathy.

HYPOTHESIS 1: Patient outcomes will be equivalent between the two injection techniques.

1.1 Compare the difference in the primary outcome measure between the two patient groups: numerical pain rating scale (averaged over the past 24 hours) at two months.

1.2 Compare the difference in secondary outcome measures between the two patient groups: numerical pain rating scale (averaged over the past 24 hours) at 2 weeks and 4 months; neck disability index, EQ-5D, and work ability index at 2 weeks, 2 months, and 4 months.

SPECIFIC AIM 2: Compare complication rates between the two injection techniques.

HYPOTHESIS 2: No difference will be seen in complication rates between the two injection techniques.

2.1 Determine the frequency of minor and major adverse events for each group immediately post-procedure and at 2 days after the procedure.

SPECIFIC AIM 3: Determine the technical success rate, defined as the spread of the contrast epidurogram into the neuroforamen, for each of the two injection techniques.

HYPOTHESIS 3.1: The contrast epidurogram will extend into the neuroforamen more frequently with the lateralized interlaminar approach than with the transforaminal approach.

3.1 Determine the frequency of contrast spread into the neuroforamen for each group.

HYPOTHESIS 3.2: Inadvertent intravascular injection will occur more frequently with the transforaminal approach.

3.2 Determine the frequency of inadvertent intravascular contrast injections for each group.

Background & Significance

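### The 0.99 non-inferiority power assumes LILESI is 25 points better; if the two techniques are equal, as Hypothesis 1 states, it is about 0.3 (one-sided 0.05) or 0.2 (one-sided 0.025)

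*Combined protocol and SAP*

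**What the plan says.** The Purpose of the Study section gives a central hypothesis that LILESI "will exhibit superior or equivalent efficacy to the traditional transforaminal method". Under Specific Aim 1, the aim that carries the primary endpoint, the hypothesis is narrower: "HYPOTHESIS 1: Patient outcomes will be equivalent between the two injection techniques".

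Sample Size Determination starts from superiority, with power 0.80 and alpha 0.05, "assuming positive response rates of 45% for the TFESI group and 70% for the LILESI group". The resulting total is 116, given as 57.5 per arm. The next sentence makes the second claim: "This sample size would also give us a power of 0.99 to detect non-inferiority (i.e. equivalence between TFESI and LILESI) (non-inferiority margin 0.1". No other response rates appear anywhere, and the sidedness of the non-inferiority test is not stated.

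Patient Outcome Analysis defines response ("A reduction of 2 points from baseline on the NRS will be considered a positive response") and names the primary tests: "We will apply a difference test and a non-superiority test for binomial proportion to test the primary endpoint". It gives neither an upper equivalence bound nor a two-sided equivalence test.

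**The concern.** A power figure belongs to an assumed truth. Here the figure is labelled as power for equivalence, and equivalence is the hypothesis under Aim 1. Read together, the two passages tell the reader that if the techniques work equally well, this trial is almost certain to show it.

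The only rates available to produce 0.99 are those of the superiority scenario, in which LILESI is 25 points better. That difference is two and a half times the 0.10 margin, so it is a scenario in which the techniques are not equivalent by the plan's own yardstick. No passage gives power for the case where the rates are the same.

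At stake is how the primary result is read. A team that believes it had 0.99 power for equivalence could take a non-significant difference as confirmation of Hypothesis 1, when the trial had little chance of settling the question.

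**Working it through.** **Inputs.** From Sample Size Determination: TFESI 45%, LILESI 70%, 116 patients (58 per arm), margin 0.10, alpha 0.05. Sidedness is not given, so both one-sided 0.05 (z = 1.645) and one-sided 0.025 (z = 1.960) are shown. From Hypothesis 1: true difference zero. The common response rate is an assumption. The documents give none, so the planning range of 45% to 70% is used, with higher rates as a sensitivity check. Dropout and the interim look at p < 0.001 are ignored; neither would raise power materially.

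**Step 1: the superiority sample size.** Unpooled formula, two-sided 0.05, power 0.80:

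n per arm = (1.96 + 0.8416)² × (0.45×0.55 + 0.70×0.30) / 0.25² = 7.849 × 0.4575 / 0.0625 = 57.45.

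This reproduces the plan's per-arm figure.

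**Step 2: the stated 0.99.** Power = Φ((d + 0.10)/SE − z), with SE = √((pT·qT + pL·qL)/58), where pT and pL are the TFESI and LILESI response rates, q = 1 − p and d = pL − pT.

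For 45% versus 70%: SE = √(0.4575/58) = 0.0888, and (0.25 + 0.10)/0.0888 = 3.94.
- One-sided 0.05: Φ(3.94 − 1.645) = 0.989.
- One-sided 0.025: Φ(3.94 − 1.960) = 0.976.

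Exact binomial enumeration gives 0.988 and 0.973. The stated figure therefore reproduces with the superiority rates and matches one-sided 0.05 best. That these rates were used is inferred from the text and this match; the plan does not say so.

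**Step 3: the same formula with equal rates (d = 0).**

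| Common rate | SE | 0.10/SE | Power, one-sided 0.05 | Power, one-sided 0.025 |
|---|---|---|---|---|
| 45% | 0.0924 | 1.082 | 0.287 | 0.190 |
| 57.5% | 0.0918 | 1.089 | 0.289 | 0.192 |
| 70% | 0.0851 | 1.175 | 0.319 | 0.216 |

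Exact enumeration of the Wald test over 45-70% gives 0.275-0.324 and 0.199-0.223, so the result does not depend on the normal approximation. Outside the planning range the exact values are 0.39 / 0.28 at 80% and 0.46 / 0.34 at 85%.

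**Step 4: how far the 0.99 depends on the advantage.** TFESI fixed at 45%:

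| LILESI better by | One-sided 0.05 | One-sided 0.025 |
|---|---|---|
| 25 points | 0.989 | 0.976 |
| 20 | 0.95 | 0.91 |
| 15 | 0.86 | 0.78 |
| 10 | 0.70 | 0.58 |
| 5 | 0.49 | 0.37 |
| 0 | 0.287 | 0.190 |

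**Step 5: equivalence taken literally.** Equivalence within ±0.10 requires the 90% confidence interval to lie inside those bounds. Its half-width is 1.645 × SE: 0.152 at 45%, 0.151 at 57.5% and 0.140 at 70%, each larger than 0.10. Exact power of two one-sided tests at 0.05 is below 0.000001 throughout 45-70%, and only 0.003 at 80% and 0.037 at 85%.

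**Step 6: the likely result if Hypothesis 1 is true.** With equal rates of 45-70%, the exact probability that the two-sided 0.05 difference test is non-significant and non-inferiority is also not shown is 0.648-0.700 (one-sided 0.05) or 0.749-0.775 (one-sided 0.025).

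**The case against.** The best defence is that power is always conditional, that the assumed rates stand in the sentence just before, and that 0.99 is right under them. On this view equivalence is loose usage for not worse: the central hypothesis allows superiority, non-inferiority is named, and a single margin is given. The arithmetic defence stands, and 0.99 does suit the superior half of the central hypothesis. The loose-usage defence does not rescue the sentence, because Hypothesis 1 says outright that outcomes are equivalent and no passage gives power for that case.

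Some further points are fair:
- The 45-70% range for a common rate is borrowed from the superiority scenario. Power is higher at more extreme rates, but still far from 0.99 at 80% or 85%.
- The dependence on 25 points is a gradient. Power is still 0.95 at 20 points (one-sided 0.05), so the figure needs an advantage of about 25 points or more.
- The upper bound of +0.10 in the equivalence check is not in the plan. It simply mirrors the stated margin to test the gloss.
- Wording changes do not make Hypothesis 1 testable as equivalence. For scale, 80% non-inferiority power at equal rates would need 260 (at 70%) to 307 (at 45%) per arm at one-sided 0.05, or 330 to 389 at one-sided 0.025, against 58 planned.
- The unstated sidedness and the non-superiority label are separate defects. They leave the test behind the 0.99 poorly defined but do not cause the power problem.

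**Conclusion.** The concern holds, and the sentence must be corrected. The 0.99 is a correct non-inferiority power for a truth in which LILESI is 25 points better, presented as power for equivalence. Under the truth that Hypothesis 1 describes, it overstates non-inferiority power roughly three- to fivefold (0.99/0.32 ≈ 3.1; 0.99/0.19 ≈ 5.2), and the trial would most often end without a conclusion.

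This rests on 58 analysed patients per arm, a margin of 0.10 on the response-rate difference, and a common response rate between 45% and 70%. The direction of the finding does not depend on the choice of sidedness or on the approximation. The superiority sample size is unaffected.

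**What to change.** 1. State whether the non-inferiority test is one-sided 0.05 or 0.025.
2. Replace the power sentence with one that names both scenarios, keeping the figures that match the chosen sidedness. For example: *With 116 patients and a margin of 0.10, power for non-inferiority is 0.99 [one-sided 0.05] or 0.98 [one-sided 0.025] if response is 45% with TFESI and 70% with LILESI, and about 0.29-0.32 or 0.19-0.22 respectively if the two rates are equal at 45-70%.*
3. Delete the parenthesis that equates non-inferiority with equivalence. State that equivalence within ±0.10 cannot be shown with 116 patients at the planning rates, and cross-refer Hypothesis 1 to that statement.
4. In Patient Outcome Analysis, reconcile the non-superiority test with the non-inferiority test that was powered.
5. Report the risk difference with its confidence interval against −0.10, and say that a non-significant difference test will not be read as equivalence.

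The cost is protocol and SAP wording only. No patients are added and the superiority calculation stays as it is. The downside is a less favourable stated power.
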